A potential use of AposTherapy as a replacement for traditional physical therapy may yield a less costly, more effective therapy with better adherence. Problems with traditional therapy include poor patient adherence (patients often do not complete the sessions and have very poor adherence (about 50-60%) to home therapy programs [7]), added cost of travel (which may be more than \$100 per session for ambulette or access-a-ride for eligible patients), and the lack of continuation in an ongoing exercise program, leading to relapse and need for retreatment. Additionally, access to physical therapy is limited for many patients since there are not enough available outpatient therapy services to meet the needs of all patients. Finding an alternative exercise program that will increase adherence, decrease total therapy visits, and improve patient's outcomes with decreased dependence on pain medications is a high priority from both patient care and cost management perspectives.

AposTherapy potentially overcomes many of these issues with improving/modifying abnormal biomechanics (therefore decreasing pain), and a home-based exercise program utilizing footwear that causes exercise with normal activity by promoting perturbation. This biomechanical approach may significantly reduce pain and improve function in patients with

knee OA. Capitalizing on the reported excellent adherence and clinical benefit of AposTherapy in patients with significant knee OA, we propose to evaluate the biomechanical exercise (wearing an appropriately calibrated shoe at home for a prescribed amount of time each day) as a conservative treatment that may supplement or supplant traditional pain medications, interventional pain procedures and physical therapy in an at-risk urban inner city population with knee OA.

2. Study objective

The purpose of the current study is to evaluate the effect of this home-based biomechanical device and treatment (AposTherapy) in knee OA population. This will be a randomized single blinded (evaluator) trial of conventional physical therapy versus AposTherapy in patients with knee OA treated for one year.

In order to assess the efficacy of the intervention with AposTherapy on our patient population, a set of primary and secondary outcome measures will be defined:

3. Outcome measures

3.1. Primary outcome measures:

- Pain and function at 1 year following treatment initiation

3.2. Secondary outcome measure:

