4.6. Sample size

Our target recruitment is 147 individuals randomly assigned to one of two groups; traditional physical therapy or AposTherapy, on a 1:2 ratio. A sample size of 147 patients will yield 80% power to detect an expected difference on the WOMAC pain scale, with components measured on VAS scales from 0 to 10 and a summary score standardized to also range from 0 to 10, of 1.5 at a 2-sided alpha of 0.05. The difference corresponds to a

[figure not shown]
clinically meaningful moderate effect size of 0.4 standard deviation units assuming a typical standard deviation of 2.65. Anticipating an attrition rate of 10%, we aim at recruiting 162 patients for the trial (54 patients will be assigned to traditional physical therapy and 108 patients will be assigned to AposTherapy)

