4.8. Assessment time points

Visits for evaluation will be done in a blinded fashion with independent evaluators who will perform all follow-up evaluations. Patients will have all outcome measures on initial entry into the study (pre-treatment), at 4 weeks, 8 weeks, 12 weeks, 24 weeks and 52 weeks after entry into the study.

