4.9. Outcome measures

Primary study outcome:

- Western Ontario and McMaster Universities (WOMAC) pain scale at one year.
- WOMAC function scale at one year

Secondary study outcome: at: Pre-treatment, 4 weeks, 8 weeks, 12 weeks, 24 weeks, 52 weeks.

- WOMAC pain and function subscale
- PROMIS Pain Interference and Physical Function
- Costs: Assessment of total utilization and cost from resource utilization monitored via the CMO
- MOS item of the Short Form (SF)-36
- Spatio-temporal gait assessment including gait velocity, step length, single limb support and limb symmetry measured by Zeno Walkway ®
- 6-min walk test
- Blood pressure and resting heart rate

- Treatment adherence: Measured via attendance at sessions of therapy (conventional therapy), hours of use of AposTherapy (Patient to have step counter)
- Overall activity and sleep patterns (both arms (via FitBit Charge HR (<http://www.fitbit.com/chargehr#i.f9n1ye1ehxd30p>) motion sensor worn for one week after each evaluation session, mailed back via prepaid mailer at the end of the week.)

5. Statistical analysis

All demographic data will be reported as mean standard deviations and average. Data from primary and secondary outcome measures will be checked for skewness using Fisher-Pearson coefficient of skewness. ANOVA or Kuskal-Wallis test will be applied depending on normality of data. All statistical analysis will be conducted using IBM SPSS Statistics Ver.24.

6. Benefits

- Participants will all have physical therapy for their knee
- AposTherapy involves fewer visits to the physical therapy center thus allowing individuals more time at home and lower transportation costs
- AposTherapy is done at home and more convenient
- AposTherapy will be provided for free for participants.

7. Risks

- Muscle soreness associated with exercise
- Minimal fall risk with use of new footwear device and exercise

8. Subject Reimbursement

Participants will be reimbursed a total of \$40 at each assessment point (pre-treatment, at 4 weeks, 8 weeks, 12 weeks, 24 weeks and 52 weeks after entry into the study). Participants will

receive \$95 reimbursement for their time at the completion of the study after return of all devices and materials. This will apply to all arms of the study.

Study schedule:

Study Periods	Screening	1	2	3	4	5	6	7
Visit		1	2	3	4	5	6	7
Time (week)	-2	0	4	8	12	24	52	
Patient Information and Informed Consent	X							
Demographics	X							
Medical History	X							

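### The one-year WOMAC tests can use only patients with a week-52 score and ignore baseline and four other scheduled visits; if dropout differs between arms, the comparison is biased

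*Combined protocol and SAP*

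**What the plan says.** Apart from demographic summaries and the software version, Section 5 contains two statements: "Data from primary and secondary outcome measures will be checked for skewness using Fisher-Pearson coefficient of skewness", and "ANOVA or Kuskal-Wallis test will be applied depending on normality of data". It names no analysis population, missing-data rule, baseline adjustment, longitudinal model or sensitivity analysis, and no other section supplies them.

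Section 4.9 gives the primary outcomes as "Western Ontario and McMaster Universities (WOMAC) pain scale at one year" and "WOMAC function scale at one year". Section 4.8 has all outcome measures taken at entry and "at 4 weeks, 8 weeks, 12 weeks, 24 weeks and 52 weeks after entry into the study". Section 4.9 lists WOMAC pain and function again under "Secondary study outcome: at: Pre-treatment, 4 weeks, 8 weeks, 12 weeks, 24 weeks, 52 weeks".

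Attrition appears only in the sample size (synopsis and Section 4.6): "Anticipating an attrition rate of 10%, we aim at recruiting 162 patients for the trial". This is one overall rate, not split by arm. Section 1 says of traditional therapy that "patients often do not complete the sessions and have very poor adherence", and reports excellent adherence with the device.

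**The concern.** A two-group test on a single time point drops every patient whose value at that time point is missing. The plan does not say that this is intended, but it is what happens when the named tests are run on a one-year endpoint.

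If the patients lost from one arm differ from those lost from the other, the remaining patients no longer give a fair comparison, and the loss of randomised patients goes unremarked in the primary result. The direction is not known in advance. If patients in more pain leave, and physical therapy loses more of them, the result flatters physical therapy. The opposite pattern flatters the device.

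The scores that could reduce this problem are already scheduled, so the choice of test discards information the trial will hold. Leaving out baseline also gives up precision, whatever the dropout pattern.

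**Working it through.** **1. What the tests can use.** ANOVA and Kruskal-Wallis on week-52 WOMAC need a week-52 value. Reading ANOVA as conventional repeated-measures ANOVA does not help, because that drops patients with any missing visit.

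**2. The plan's own attrition figure.** 147 × 1.10 = 161.7, giving the stated 162 (54 + 108). Dividing instead, 147 / 0.9 = 163.3, gives 164; the difference is immaterial here. Ten per cent of 162 is 16.2 patients without a week-52 value.

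**3. When completers mislead.** In each arm let p be the proportion missing, and g the mean week-52 score of dropouts minus that of completers. The completers' mean equals the arm's true mean minus p × g. With no true effect, the bias in device minus physical therapy (PT) is

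bias = p(PT) × g(PT) − p(device) × g(device).

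This is zero when p and g match across arms, so dropout that depends on pain is not enough on its own. By hand, with assumed g of 1 to 2 points:

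- 13% PT / 7% device, same g in both arms: 0.06 × 1 = 0.06 to 0.06 × 2 = 0.12 points.
- 13% / 7%, g = 0 in the device arm: 0.13 × 1 = 0.13 to 0.13 × 2 = 0.26 points.
- 20% / 5%, same g (10% overall, since 54 × 0.20 + 108 × 0.05 = 16.2): 0.15 to 0.30 points.

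**4. Simulation.** From Section 4.6: 54:108 allocation, SD 2.65, target difference 1.5. Assumed, because the documents give no values: no true effect; correlation 0.6 between baseline and later scores and 0.75 between weeks 24 and 52; dropout after week 24 of 13% PT and 7% device (54 × 0.13 + 108 × 0.07 = 14.6 patients, 9% overall); and the slope of dropout on week-24 pain. Positive bias makes the device look worse than it is.

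| Slope (logits per SD) | Same mechanism in both arms | Only PT dropout depends on pain |
|---|---|---|
| 0.5 | 0.06 | 0.12 |
| 1.0 | 0.10 | 0.23 |
| 1.5 | 0.13 | 0.30 |

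Simulation error is about 0.01. As shares of 1.5 points, the extremes are 0.06 / 1.5 = 4% and 0.30 / 1.5 = 20%. Type I error stayed between 4.5% and 5.8% with the same mechanism in both arms. It was 7.6% and 10.0% at slopes 1.0 and 1.5 when only PT dropout depended on pain.

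At 10% dropout in both arms, the bias is about zero with the same mechanism and about 0.18 if only one arm's dropout depends on pain. Equal rates alone are therefore not a safeguard.

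**5. Using the other scores.** A likelihood estimate that uses baseline and week 24 had bias of 0.01 or less in these scenarios. Its standard error was about 0.37 against 0.46 for completers. Most of that gain comes from baseline: 0.46 × √(1 − 0.6²) = 0.46 × 0.8 = 0.37. Baseline adjustment among completers alone still leaves about half the bias (0.16 of 0.30), so the intermediate visits are needed as well.

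**The case against.** A reader might infer from Section 1 that dropout is likely to differ by arm. The documents do not support that. The passage concerns finishing therapy sessions and keeping up a home programme, not attending outcome visits. Assessments are made by independent evaluators in both arms, and Section 8 pays all arms $40 per assessment and $95 at completion. Dropout may differ; no more can be said.

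A reader might also take the top of the range, about 0.3 points, as the expected error. It needs a steep slope in one arm and purely random loss in the other. With the same mechanism in both arms the bias is 0.13 or less and type I error is close to nominal.

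The simulation also suits the proposed method: dropout depends on a score that was observed, and every dropout has a week-24 value. Section 4.7 places therapy sessions in the first 4 to 8 weeks, so someone who left then would have no week-24 score, and leaving could depend on pain never recorded. Neither case was tested. This stands, and it is why a sensitivity analysis belongs in the plan.

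Finally, a mixed model is not the only sound choice. Multiple imputation using the other visits, with baseline adjustment, would serve equally well.

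None of this supplies the missing rule or justifies leaving out data already scheduled.

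**Conclusion.** The point holds as a cheap improvement. The primary tests named in Section 5 leave out patients without a week-52 WOMAC, about 16 of 162 at the planned attrition, and make no use of baseline or four other follow-up visits.

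Under the assumed 13% / 7% dropout, the resulting bias is about 0.06 to 0.13 points if the same mechanism acts in both arms, and about 0.12 to 0.30 if only physical therapy dropout depends on pain. It is about zero if rate and mechanism match. The dropout rates by arm, slopes and correlations are all assumptions, so the documents establish neither the presence nor the direction of bias in this trial. The precision gain does not need differential dropout; it rests on the assumed baseline correlation.

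The SD of 2.65 and the 1.5-point target are taken as stated. They imply 1.5 / 2.65 = 0.57 SD, not the 0.4 SD also given in Section 4.6, which is a separate matter to reconcile.

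**What to change.** In Section 5, replace the skewness-driven choice of test for the two primary endpoints with the following:

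- Analyse all randomised patients in their assigned arm.
- Fit a mixed model for repeated measures to WOMAC pain, and another to WOMAC function, at weeks 4, 8, 12, 24 and 52, with the baseline value as covariate and an arm-by-visit interaction.
- Take the week-52 contrast between arms as the primary estimate.
- Accept baseline-adjusted analysis with multiple imputation from the other visits as an equivalent. State how patients with no post-baseline score are handled, since they add nothing to the mixed model's contrast.
- Add one delta-adjusted sensitivity analysis that makes dropouts' unobserved scores progressively worse, because leaving may depend on pain that was not recorded.
- Report the number missing at week 52 by arm.

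The study schedule table names VAS and ODI instead of WOMAC. It should be reconciled with Sections 4.8 and 4.9 so that WOMAC collection at every visit is unambiguous.

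The cost is plan wording, fixed before outcome data are seen by arm, and a little more analysis work. The named software can fit the model, and no new visits or data are needed. The downside is that the primary analysis then relies on a missing-at-random assumption, which the sensitivity analysis probes.

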4.1. Trial Design

Single blinded (evaluator), single-center, randomized controlled trial.

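### Section 5 gives the one-year WOMAC endpoints no baseline term and does not say which form of the score is analysed; baseline adjustment would gain precision, provided the baseline is taken before allocation is known

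*Combined protocol and SAP*

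**What the plan says.** Section 4.9 names two primary outcomes: "Western Ontario and McMaster Universities (WOMAC) pain scale at one year", and the WOMAC function scale at the same time.

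Section 5 is the only analysis text. It says "Data from primary and secondary outcome measures will be checked for skewness using Fisher-Pearson coefficient of skewness", and then "ANOVA or Kuskal-Wallis test will be applied depending on normality of data". It mentions no covariate, change score or repeated-measures model, and no effect estimate.

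Baseline WOMAC is nevertheless planned:
- Section 4.8: "Patients will have all outcome measures on initial entry into the study (pre-treatment", followed by the visits at weeks 4, 8, 12, 24 and 52.
- Section 4.9: "Secondary study outcome: at: Pre-treatment, 4 weeks, 8 weeks, 12 weeks, 24 weeks, 52 weeks". WOMAC pain and function come first in the list beneath.
- Study schedule: the row for secondary outcome measures is marked from week 0. Through 4.9 that row includes WOMAC.

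On blinding, Section 4.1 says "Single blinded (evaluator), single-center, randomized controlled trial". As extracted, the study schedule marks randomisation in the screening column (week -2) and outcomes from week 0.

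**The concern.** A patient's WOMAC score at entry usually predicts part of the score a year later. When it is left out, that predictable variation stays in the error term and the interval for the treatment difference is wider than it need be. The measurement is already being paid for.

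Section 5 also leaves the analysed quantity open. An ANOVA of the week-52 value, of the change, or over repeated visits would each fit its wording, and these differ in precision. Naming one before the data are seen removes that choice.

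**Working it through.** **Inputs.** From Section 4.6 and the synopsis: 49 and 98 patients, SD 2.65 for WOMAC pain, difference 1.5 points, two-sided alpha 0.05. Assumed, because the documents do not give them:
- Baseline to week-52 correlation r of 0.3 and 0.5, with 0.7 as an optimistic upper value. Entry requires a VAS pain score of at least 3 cm, which may narrow the baseline range and lower r.
- Ratio k of baseline SD to week-52 SD, taken as 1 or 0.7.

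**Step 1: the plan's own figure.** Section 4.6 describes 1.5 points as a "clinically meaningful moderate effect size of 0.4 standard deviation units assuming a typical standard deviation of 2.65". But 1.5/2.65 = 0.566, and 0.4 × 2.65 = 1.06 points. With 49:98 and the noncentral t, power is 89.5% for 0.566 SD and 62.2% for 0.4 SD. Neither is the stated 80%, which 147 patients reach at about 0.49 SD (1.30 points). That contradiction is a separate matter; both targets are carried below.

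**Step 2: unadjusted week-52 comparison.** SE = 2.65 × √(1/49 + 1/98) = 0.464. The 95% CI half-width is t × SE = 0.916, or 0.92 points.

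**Step 3: ANCOVA on baseline.** The variance is multiplied by (1 − r²), and one degree of freedom is lost. The equivalent unadjusted total is 147/(1 − r²).

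| r | Variance factor | Equivalent unadjusted N | Half-width (points) | Power, 0.4 SD | Power, 1.5 points |
|---|---|---|---|---|---|
| none | 1.00 | 147 | 0.92 | 62.2% | 89.5% |
| 0.3 | 0.91 | 162 | 0.87 | 66.3% | 92.1% |
| 0.5 | 0.75 | 196 | 0.79 | 74.6% | 96.0% |
| 0.7 (optimistic) | 0.51 | 288 | 0.65 | 88.9% | 99.4% |

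No SD is given for WOMAC function, so only the variance factors carry over to it, and only for the same r.

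**Step 4: if ANOVA means change from baseline.** The variance relative to the unadjusted week-52 test is 1 + k² − 2rk. It exceeds the ANCOVA factor by (k − r)², so in large samples ANCOVA is never less precise, and the gain vanishes when r = k.
- k = 1: change-score factor 1.40 at r = 0.3 and 1.00 at r = 0.5. ANCOVA cuts the variance by 35% (0.91/1.40 = 0.65) and 25% (0.75/1.00).
- k = 0.7: factor 1.07 and 0.79. The cut is 15% (0.91/1.07 = 0.85) and 5% (0.75/0.79 = 0.95). At r = 0.7 it is 0.51/0.51, no gain.

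**Step 5: if baseline is given after the patient knows the arm.** Suppose this shifts baseline WOMAC in one arm by s = 0.5 points (an assumption with no basis in the documents). The ANCOVA difference is then biased by (r/k) × s, and root mean squared error = √(bias² + 0.464² × (1 − r²)). The unadjusted value is 0.464.

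| r | Bias, k = 1 | RMSE, k = 1 | Bias, k = 0.7 | RMSE, k = 0.7 |
|---|---|---|---|---|
| 0.3 | 0.15 | 0.467 | 0.21 | 0.491 |
| 0.5 | 0.25 | 0.473 | 0.36 | 0.537 |
| 0.7 | 0.35 | 0.482 | 0.50 | 0.600 |

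ANCOVA is worse in every cell. Setting the two errors equal gives s/k = 0.464. ANCOVA therefore loses its advantage once the shift exceeds 0.46 points (k = 1) or 0.464 × 0.7 = 0.32 points (k = 0.7). A smaller shift still leaves some bias.

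**The case against.** The strongest reply is that nothing here is wrong: the unadjusted comparison is valid under randomisation, and the gain rests on a correlation that the documents do not give. Both statements stand. They make this a precision improvement and set its size as a range.

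A second reply is that adjustment seldom decides whether 80% power is reached. That also stands. For 1.5 points with SD 2.65 the target is met unadjusted; for 0.4 SD it is still missed at r = 0.3 and 0.5, and is passed only at the optimistic 0.7. A reader might infer that leaving out baseline makes the trial underpowered. The documents do not support this: the 62% comes from the conflict between 0.4 SD and 1.5/2.65 in Section 4.6.

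Third, Section 5 may intend a change score or repeated measures. It excludes neither. Against a change score the gain can shrink to almost nothing, and no figure was worked out against repeated-measures ANOVA or Kruskal-Wallis. What stands regardless is that the analysed quantity is unspecified.

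Fourth, a baseline given after allocation could make ANCOVA the worse choice. Step 5 bears this out for the assumed shift, so the recommendation has to be conditional.

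**Conclusion.** The point holds as an inexpensive improvement in precision and clarity. At an assumed r of 0.3 to 0.5, adjustment removes 9% to 25% of the variance of an unadjusted week-52 comparison and narrows the WOMAC pain half-width from 0.92 to between 0.87 and 0.79 points at 49:98. Against a change score the gain is smaller when the baseline SD is below the week-52 SD, and may be close to zero.

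Three stronger readings are not supported:
- That the planned analysis is biased. The randomised comparison needs no baseline term to be unbiased.
- That WOMAC is not collected at baseline because the schedule's named outcome row is VAS and ODI. The secondary-outcome row at week 0, read with 4.8 and 4.9, covers it.
- That baseline is known to follow allocation. The extracted table suggests this order, but its column alignment may be unreliable, and the wording of 4.8 does not settle the order relative to randomisation.

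The VAS and ODI label and the lack of a rule for missing week-52 scores are separate matters and no part of this conclusion.

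**What to change.** In Section 5, state that the primary analysis of each WOMAC endpoint is an ANCOVA of the week-52 score with arm and that scale's own baseline score as terms. Patients are analysed as randomised, and the adjusted mean difference is reported with its 95% CI. Keep Kruskal-Wallis as a supportive analysis.

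Make this conditional on timing. State in 4.8 and in the schedule that baseline WOMAC is completed before the allocation is revealed. If that is not done, keep the unadjusted week-52 comparison as primary and report the ANCOVA as supportive.

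The cost is a few sentences and a check of the schedule, with no new data, visits or patients. The order of baseline assessment and randomisation changes only if baseline is at present taken after allocation.

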- Total healthcare utilization and costs of physical therapy and AposTherapy will be assessed, including physical therapy, ED visits, pharmacological pain treatments, joint injections, imaging studies, surgical procedures, physician visits related to knee pain and total physician visits
- Pain medication consumption
- Quality of life
- Gait assessment
- 6-min walk test

- Blood pressure and resting heart rate
- Adherence to treatment - AposTherapy group (Patient to have step counter permanently attached to AposTherapy device)
- Overall activity and sleep patterns, both groups. Will be measured via FitBit Charge HR (<http://www.fitbit.com/chargehr#i.f9n1ye1ehxd30p>) motion sensor worn for one week after each evaluation session, mailed back via prepaid mailer at the end of that week.

4. Materials and Methods

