During the first assessment the biomechanical device (AposTherapy device) will be individually calibrated to each patient by a physiotherapist certified in AposTherapy treatment methodology. The principle of device calibration is to achieve minimal pain while walking. For example, in knee OA with medial compartment disease, the pod-element under the hindfoot is shifted laterally from the neutral position. This shifts the center of pressure (COP) in the foot laterally, thereby reducing the magnitude of the knee adduction moment acting on the knee joint. This is done until the patient reports minimal pain during initial contact. The forefoot pod-element is shifted medially from the baseline position until the patient reports minimal pain during mid-stance to toe-off. Once the desired alignment is achieved, the patient should report immediate pain relief while walking. Following calibration patients will receive home-based exercise guidelines. During the first three weeks patients will be instructed to wear the calibrated biomechanical device for 30 minutes, while doing their daily activities (overall accumulating 10-15 minutes' walk). Patients will be instructed to gradually increase their wearing time reaching 2 hours a day following 3 months of treatment. After three months, patients will be encouraged to add outdoor walking, starting with 10 minutes and reaching 30 minutes a day. Patients will be asked to come back to follow-up meetings at the clinical center after 4 weeks, 8 weeks, 12 weeks, 24 weeks and 52 weeks. During these follow-up meetings patients will be re-assessed by the Apos therapist and, if needed, the biomechanical device will be re-calibrated.

Group 2: Traditional physiotherapy

Physical therapy for knee osteoarthritis is provided at Department of Rehabilitation Medicine, Moses Division, three times a week for 4 to 8 weeks (up to 20 sessions) depending on the progression of the subject. Each session takes about 1 hour. Physical therapist will follow the standard of care protocol available at our institution with minor adjustment as needed (Appendix 1).

Typical physical therapy regimen for knee OA includes strengthening, stretching exercise, therapeutic modality and education.

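### Section 5 lets observed skewness choose between ANOVA and Kruskal-Wallis with no cut-off and no effect estimate, so the primary WOMAC test is not fixed and nothing prespecified estimates the 1.5-point pain difference or the difference in mean cost

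*Combined protocol and SAP*

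**What the plan says.** Section 5 is the whole analysis plan. It starts with a diagnostic: "Data from primary and secondary outcome measures will be checked for skewness using Fisher-Pearson coefficient of skewness". The test follows from it: "ANOVA or Kuskal-Wallis test will be applied depending on normality of data". Means and standard deviations are promised for demographic data only. No cut-off, between-arm estimate, interval or separate method for cost appears there or elsewhere.

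The primary outcomes in Section 4.9 are WOMAC pain and WOMAC function at one year. Section 4.6 states that 147 patients "will yield 80% power to detect an expected difference on the WOMAC pain scale" of 1.5 points, with a standard deviation of 2.65.

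Cost is a secondary outcome. Section 3.2 says "Total healthcare utilization and costs of physical therapy and AposTherapy will be assessed" and counts ED visits and surgery among the components. Section 4.9 says "Costs: Assessment of total utilization and cost from resource utilization monitored via the CMO". Section 1 gives as motivation that AposTherapy "may yield a less costly, more effective therapy with better adherence".

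**The concern.** A plan should fix the primary test and the quantity it estimates before the data are seen. Here both depend on a sample statistic with no stated threshold. With two arms, ANOVA compares means and Kruskal-Wallis compares ranks, so the switch changes the question as well as the test. On the rank branch a p-value would have no estimate beside it to set against the planned 1.5 points.

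For cost, a payer's total bill is mean cost times number of patients, so a claim of lower cost is naturally a claim about means. A rank test need not agree with the means when the arms' cost distributions differ in shape. A significant result could then be read as one arm costing less when mean costs are equal or differ the other way.

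**Working it through.** **The plan's own figure.** With 1:2 allocation, two-sided alpha 0.05 and 80% power, control n = 1.5 × (1.960 + 0.842)² / d².
- Stated inputs: d = 1.5/2.65 = 0.566, so n = 37 and the total is 111. At 49:98 the power is Φ(0.566 × √(49×98/147) − 1.960) = Φ(1.275) = 89.9%.
- Stated effect size: d = 0.4 needs 222 in total, and 49:98 gives 62.8%.

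The stated 80% at 147 is therefore not reproduced. That is a separate matter. What counts here is that the sizing is for a difference in means.

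**WOMAC pain: does the missing cut-off matter?** From Section 4.6: SD 2.65, difference 1.5, 49 v 98. Assumed: the one-year means and a beta shape scaled to 0–10. With m = mean/10 and v = 0.265² = 0.0702, k = m(1−m)/v − 1, a = mk and b = (1−m)k. At mean 2.0, k = 0.16/0.0702 − 1 = 1.28, a = 0.26 and b = 1.02. Skewness is computed on all 147 values.

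| Means, PT v AposTherapy | Skewness > 0.5 | Skewness > 1.0 | Tests disagree | Power, ANOVA v KW | AposTherapy scores below 0.5 |
|---|---|---|---|---|---|
| 3.5 v 2.0 | 100% | 48.8% | 10.8% | 89 v 99% | 47% |
| 4.0 v 2.5 | 95.9% | 2.8% | 7.5% | 88 v 96% | 32% |
| 4.5 v 3.0 | 53.8% | 0% | 4.2% | 89 v 93% | 21% |
| 5.0 v 3.5 | 8.0% | 0% | 2.2% | 89 v 90% | 13% |

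The unstated cut-off can decide the primary test. The first two rows rest on heavy piling-up near zero. A different assumed shape (normal, mean 3, SD 2.65, clipped to 0–10) passes 0.5 in 35% of samples and 1.0 in almost none, so the dependence on the cut-off remains.

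With no true difference, taking whichever test is significant gives 5.4–6.9% error. Applying the switch at a fixed 0.5 or 1.0 gives 4.9–5.5%.

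**Cost: which branch?** No cost distribution is given, so lognormal is an assumption. At log-SD 1.0 or more, skewness exceeds 1 in practically all trials and 2 in about 93–99%. At log-SD 0.5 it exceeds 1 in 89.1% and 2 in 16.3%. Kruskal-Wallis is probable, not certain.

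**Cost: ranks against means.** Let the arms have equal means and log-SDs s_P (physical therapy) and s_A (AposTherapy). Then:
- median ratio A/P = exp(−(s_A² − s_P²)/2)
- P(A < P) = Φ((s_A² − s_P²) / (2√(s_A² + s_P²)))

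At 1.0 v 1.5 the median ratio is exp(−0.625) = 0.54 and P(A < P) = Φ(1.25/3.606) = 0.636, although the means are equal. Rejection rates at p < 0.05, 49 v 98:

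| Log-SD, PT v AposTherapy | Median ratio | P(A < P) | Kruskal-Wallis | Welch |
|---|---|---|---|---|
| 1.0 v 1.0 | 1.00 | 0.500 | 4.9% | 5.2% |
| 1.0 v 1.1 | 0.90 | 0.528 | about 8% | about 5% |
| 1.1 v 1.0 | 1.11 | 0.472 | about 9% | about 6% |
| 1.0 v 1.2 | 0.80 | 0.556 | 18.7% | 4.2% |
| 1.2 v 1.0 | 1.25 | 0.444 | 21.0% | 7.4% |
| 1.0 v 1.3 | 0.71 | 0.583 | 36.5% | 3.8% |
| 1.3 v 1.0 | 1.41 | 0.417 | 38.1% | 8.8% |
| 1.0 v 1.5 | 0.54 | 0.636 | 78.9% | 5.4% |
| 1.5 v 1.0 | 1.87 | 0.364 | 75.4% | 11.6% |

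From 1.0 v 1.2 outward, almost all rank rejections rank the wider arm as cheaper. The last two rows are extreme: one arm's SD is √((e^2.25 − 1)/(e − 1)) = 2.2 times the other's.

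**The case against.** The strongest reply has four parts.

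**The primary test suffers little measurable harm.** This stands. Error stays near 5%, and under the planned difference Kruskal-Wallis has equal or higher power in the assumed shapes, so most disagreements between the tests are extra power and not mistakes. A reader might infer that the switch materially inflates the false-positive rate. The figures do not support that. The unfixed test and the missing estimate remain.

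**The cost harm is assumed.** This also largely stands. The documents give no cost distribution, and the 75–79% rates need a very large difference in spread. A reader might infer that the rule is tilted towards finding AposTherapy cheaper. The documents do not show which arm would be more spread out: physical therapy is given "three times a week for 4 to 8 weeks (up to 20 sessions) depending on the progression of the subject", while Section 1 says "patients often do not complete the sessions". The runs point either way, depending on which arm is wider.

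**Mean cost as the target is inferred.** True. Cost is secondary and is only to be assessed, and the cost-saving argument is background. Nothing forbids reporting arm means, which can be computed from the data collected. The gap is that this is not prespecified. The rank rejections are not errors in themselves, since the distributions do differ. They mislead only if read as evidence on means.

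**The replacement has weaknesses of its own.** It does, and they are listed with the fix.

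**Conclusion.** The point holds, and it should be dealt with before analysis. For the primary outcomes it rests on the text alone: the test is chosen after the data are seen, by an unstated threshold, and no treatment effect is estimated. The simulations show only that a cut-off of 0.5 or 1.0 can change which test is used; how often depends on the assumed score distribution.

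For cost the point is secondary and conditional. It needs right-skewed cost (plausible from its components), mean cost as the quantity of interest (inferred), and arms that differ in shape (unknown). With the same shape there is no problem, with a small difference the effect is slight, and only a large difference gives the high rates. The documents do not support saying that the trial will reach a wrong cost conclusion, or in which direction one would fall.

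**What to change.** Reword Section 5:
1. Remove the skewness-triggered choice of test.
2. For WOMAC pain and WOMAC function at 52 weeks, prespecify the AposTherapy minus physical therapy mean difference with a 95% confidence interval, and name the single model that produces it. For pain this matches the 1.5 points in Section 4.6.
3. For total cost per patient over 52 weeks, prespecify the difference in arithmetic means with a 95% interval that does not assume equal variances (Welch, or a symmetric bootstrap-t resampled within arm).
4. Keep rank tests as sensitivity analyses, and do not report them as evidence on mean cost.

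The Resources table mentions historical costs, but patient-level data are not shown, so the fix should not depend on them.

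The change needs no new data and little extra analysis work. Its downsides, in the same assumed settings, are:
- The cost interval is wide: median Welch width 812 to 1,089 on a mean of 1,000, a half-width of about 41–54%.
- Its coverage can fall to about 88–89% if the smaller arm has the heavier tail.
- A mean comparison has less power than a rank test for a consistent saving: 29.1% v 49.7% for a 30% saving with the same shape, and 12.3% v 61.2% for a fixed saving of 200 on a mean of 1,000 (log-SD 1.0).
- On WOMAC, if scores pile up near zero, power is about 88–90% against 90–99% for Kruskal-Wallis.
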